## ADDRESSING HETROGENITY OF TREATMENT EFFECTS (HTE)

Analyses of HTE will allow us to gain insight into whether the examined associations are consistent across clinically relevant populations (e.g., across key demographic groups). **[HT-1]**. To assess possible HTE, we propose to repeat the primary analyses for all 3 aims within each of the subgroups defined by race/ethnicity (e.g., non-Hispanic black, Hispanic, non-Hispanic white), age (adolescents will be analyzed separately; also <65 years and 65 years),  $\geq$  baseline BMI ( $\geq 50$  vs  $< 50$  kg/m $^2$ ), baseline smoking status prior to surgery (current, former, other), and comorbidity groups (e.g., baseline diabetes) or comorbidity index score quartiles **[HT-2, RQ-4]**. When there are two subgroups (e.g., BMI  $\geq 50$  vs. BMI  $< 50$  kg/m $^2$ ), we will examine the difference between the subgroup-specific effect estimates (mean difference in Aim 1, and log (hazard ratio) in Aims 2 and 3). The variance of the difference is the sum of the variances for the subgroup-specific effect estimates as the two effect estimates are independent. The standardized difference is expected to follow a normal distribution asymptotically. When there are more than two

subgroups, the differences between the effect estimate from a reference subgroup and the other subgroup-specific effect estimates, after appropriate linear transformations, follows a multivariate normal distribution asymptotically. Then the sum of the differences squared follows a chi-square distribution with the degree of freedom being the number of subgroups minus 1. A significant difference in treatment effect is detected if the corresponding p-value is  $\leq 0.05$  [HT-3]. The purpose of the HTE analysis is to explore any possible treatment effect heterogeneity instead of formal hypothesis testing. Thus we propose to use the same 0.05 significance level for all contrasts [HT-4].

For Aims 4-6, HTE analyses will be repeated for all primary and secondary outcomes in Aims 1-3.

## PLAN FOR DATA QUERIES

PCORnet has set up a distributed research model in which a main operating principle is to “send questions to the data.” Under this principle, the PCORnet Coordinating Center sends honed programming code (“queries”) to each CDRN node site, who run them, unaltered, against the Common Data Model. The study team combines the aggregate-level data from the multiple sites for analysis. Advantages over traditional pooled analysis are that data are kept in the hands of the original data holders, which decreases proprietary concerns and data breaches. Data holders transfer only minimum necessary data to a central site for analysis. In addition, data holders know their data well, facilitating cleaning and troubleshooting. In the proposed study, we will adhere to these principles while at the same time comparing findings from a fully distributed programming approach that yields only aggregate data with an approach that employs (de-identified) individual-level data. We propose a data flow system that takes advantage of, and integrates, the knowledge and expertise of the 3 main components of the study. The data flow system is shown in Figure 1, below.

The scientific teams for the studies will be responsible for defining the analytic plans including defining all outcomes, exposures, and covariates of interests. This information will be passed along to the Methods Core, which will be responsible for creating functional specifications and, working with the DRN OC Query Fulfillment Team, the technical specifications. After multiple iterations, involving the study teams, the Query Fulfillment Team will send the technical specifications to the StatLog team for code development.

Once developed, the Query Fulfillment Team will internally test queries on manufactured data sets, test the query in the pilot datamart, further beta test the query in willing datamarts, and then develop a production-level code package, based on feedback from the beta test sites. When prepared, and with confirmed data use agreements and IRB approvals from sites, the Query Fulfillment Team will transmit the code package using PopMedNet. PopMedNet™ is the query management platform for the PCORnet Distributed Research Network. In PCORnet’s distributed data environment, code is developed centrally and distributed to each partner to execute against data that are stored in a common format.

## HANDLING SPECIAL FORMS OF OBESITY

It was proposed that we should look (in ICD-9 codes) for but not exclude “special forms” of obesity, such as congenital conditions (e.g., Prader-Willi), especially in the adolescent patient population. We will

identify these patients and adjust for the conditions in the analysis. We will be hesitant to look at this group separately if it is small for practical considerations (i.e., avoiding additional analyses in the setting of limited time and resources). There is a need to develop a list of ICD-9 codes to identify these “special forms” of obesity. Below is a list of genetic disorders commonly associated with hyperphagia and the early development of obesity. The first 5 are typically present as obesity with developmental delay, while the last 5 present with obesity without developmental delay. In addition, craniopharyngioma patients (i.e. S/P surgical resection) should be included.

1. Prader-Willi
2. Albright Hereditary Osteodystrophy
3. Bardet-Biedl Syndrome
4. BDNF and TRKB Deficiency
5. SIM1 Deficiency
6. MC4R Deficiency
7. Leptin and Leptin Receptor Deficiency
8. POMC processing disorders
9. PCSK1 Deficiency
10. SH2B1 Deficiency
11. Craniopharyngioma
12. ROHHAD
13. Alstrom

## POTENTIAL ADDITIONAL SECONDARY OR EXPLORATORY ANALYSES:

Time and resources permitting, we will consider conducting a number of additional secondary or exploratory analyses for our aims; however, we currently believe that these analyses are either a) beyond the scope of our current proposal, or b) are likely to be challenged by lack of sufficient data to address the question.

- a. It was proposed that we conduct a secondary analysis among patients with a BMI between 30 and 34.9 kg/m^2 because this subgroup is of high interest to the bariatric community, especially as it relates to diabetes outcomes, but also in relation to weight loss and safety.
- b. Look at geographical variation across the US for the 3 procedures
- c. Look at hospital volume and look for correlation with outcomes and complications.
- d. For Aim 3, opportunity to analyze outcomes according to the following designation of centers: low vs. high volume centers, accredited vs non-accredited centers, academic vs community centers, teaching vs non-teaching hospitals.
- e. Consider the impact of people who are on weight loss medications after surgery and what differential impact this may have on our weight loss and diabetes outcomes across procedures, including: phentermine, orlistat (alli/Xenical), lorcaserin (Belviq), phentermine HCL/topiramate ER (Qsymia), Naltrexone HCL/bupropion HCL ER (Contrave), and Liraglutide (victoza and Saxenda). We may want to consider Metformin as well.
- f. For the adolescent group, it may be interesting to compare surgeries at adolescent centers vs. non-adolescent centers, specifically evaluating surgical complications, weight loss, and co-morbidity improvement.

## TABLES AND FIGURES

**Table 1. Common Data Model Data Tables that are Applicable to the PCORnet Bariatric Study**

PCORnet CDM Data Table	Key Information/Description of Variables	Date Range
DEMOGRAPHIC	Key demographic variables include: Age at surgery (not date of birth), sex, Hispanic ethnicity (y/n) & race are captured.	2004 – 2016* * includes information occurring 1 year before the first bariatric procedure (2005) and one year after the last bariatric procedure (2015) in the study
ENROLLMENT	Enrollment is a concept that defines a period of time during which all medically-attended events are expected to be observed. This concept is often insurance-based, but other methods of defining enrollment are possible. Key variables include: Enrollment start and end dates, and enrollment basis (which relates to how the enrollment period was defined, e.g., insurance, geography, algorithmic, encounter)	2004 – 2016
ENCOUNTER	Contains 1 record for each time a patient sees a provider in ambulatory setting or is hospitalized; multiple encounters per day are possible if they occur with different providers or in different care settings. Encounter type will be used to identify initial bariatric procedures and all subsequent complications and procedures during the follow-up period. Encounters may also be used to determine enrollment periods. Provider, facility information, and DRGs may be used to calculate propensity scores. Key variables include: encounter ID, admit date and time, discharge date and time, provider ID (a pseudoidentifier), facility location (3 digit zip code) and ID, encounter type (ambulatory, emergency, etc), discharge disposition (which can indicate death during hospitalization), and DRG.	2004 – 2016
DIAGNOSIS	Contains all uniquely recorded diagnoses for all encounters. Each diagnosis is associated with a specific patient and encounter. Diagnosis codes and associated encounter dates will be used to establish medical history prior to surgery, to calculate propensity scores, and to identify adverse events. The main focus will be on obesity related diagnoses and adverse events, such as diabetes and hypertension. Key variables include: Diagnosis date,	2004 – 2016

	Diagnosis, diagnosis type (e.g., ICD-9, ICD-10), diagnosis source, and principal diagnosis flag	
PROCEDURES	Procedure codes and associated encounter dates will be used to establish bariatric surgery dates and any reoperations or reinterventions. Key variables include: Procedure date, Procedure, Procedure type (e.g., ICD-9, ICD-10), procedure source	2004 – 2016
VITAL	Contains one record for each recorded height, weight, and blood pressure, which may be included in our propensity scores, as well ask information on smoking status, which is an important comorbid health indicator for the propensity score. Key variables include: height, weight, body mass index (BMI), systolic and diastolic blood pressure, smoking status, tobacco use & type, vital source, and dates of those measures	2004 – 2016
DISPENSING	This data table contains outpatient pharmacy dispensing information. Not all CDRNs and study sites will have access to these data, but many will. These data will be used to capture the use of diabetes treatments, and may be used to identify other comorbid health conditions and/or important co-occurring treatments, such as 2nd generation antipsychotics and obesity drugs, which can have an important impact on body weight. Key variables include: dispensing date, National Drug Code (NDC), days supply, and dispense amount	2004 – 2016
LAB_RESULT_CM	This table contains information on common laboratory measures. For this study, the laboratory measure of interest is the HbA1c for identifying diabetes and diabetes control over time. Key variables include: Lab name, specimen source, specimen date, result, and result unit	2004 – 2016
CONDITION	This data table contains information on a patient's diagnosed and self-reported health conditions and diseases. The patient's medical history and current state may both be represented. This may be used to capture medical comorbidities prior to surgery, including diabetes, as well as complications of surgery. Key variables include: condition, condition status, report date, onset date, resolve date, condition type, condition source	2004 – 2016
PRO_CM	This table contains patient-reported outcome (PRO) common measures which are standardized measures that are defined in the same way across all PCORnet networks. Each measure is recorded at the individual item level: an individual question/statement, paired with its standardized response options. While PRO data are not part of the specific aims of this study, PCORI has required us to report on the presence/absence of PRO data in our	2004 – 2016

	bariatric population to guide possible future studies. Key variables include: PRO item, PRO date, PRO response, PRO method, and PRO mode	
PRESCRIBING	This data table includes information on provider orders for medication dispensing or administration. It will be used to capture the use of diabetes drug treatments, and may be used to identify other comorbid health conditions and/or important co-occurring treatments, such as 2nd generation antipsychotics and obesity drugs, which can have an important impact on body weight. Key variables include: Rx med name, Rx order date, Rx quantity, Rx refills, RxNORM (drug identifier), Rx days supply, Rx frequency, Rx basis (dispensed or administered)	2004 – 2016
DEATH	This table contains reported mortality for patients in the study. This is critical information for Aim 3. Key variables include: death date, death date impute, death source, death match confidence	2004 – 2016
DEATH_CAUSE	This table contains cause of death information for patients in the study. This information will be used for Aim 3. Key variables include: Death cause, code, type, source, and confidence	2004 – 2016
HARVEST	This table identifies attributes associated with each site's specific PCORnet data mart implementation, which will be helpful for data quality checks. Key variables include: data mart ID, name, platform, CDM version, claims use, EHR use, management variables (indicate where imputation or obfuscation were used for variable creation), refresh date (when data were most recently loaded)	NA

**Table 2. ICD-9 and CPT-4 codes used to identify bariatric procedures from the CDM**

Code	Description	Procedure Assignment	Code type
43.82	Laparoscopic vertical (sleeve) gastrectomy	SG	ICD-9
43.89	Partial gastrectomy with bypass gastrogastrostomy; Sleeve resection of stomach	SG	ICD-9
43775	Laparoscopic sleeve gastrectomy	SG	CPT-4
44.31	High gastric bypass; Printen and Mason gastric bypass	RYGB	ICD-9
44.39	Other gastroenterostomy; Bypass gastroduodenostomy; gastroenterostomy; gastrogastrostomy; Gastrojejunostomy without gastrectomy NOS	RYGB	ICD-9
43633	Gastrectomy, partial, distal; with Roux-en-Y reconstruction	RYGB	CPT-4
43846	Gastric restrictive procedure, with gastric bypass, for morbid obesity; with short limb (less than 100 cm) Roux-en-Y gastroenterostomy	RYGB	CPT-4
43847	Gastric restrictive procedure, with small intestine reconstruction to limit absorption; with long limb (>150 cm) Roux-en-Y	RYGB	CPT-4
44.38	Laparoscopic gastroenterostomy; Bypass: gastroduodenostomy; gastroenterostomy; gastrogastrostomy; Laparoscopic gastrojejunostomy without gastrectomy NEC	RYGB	ICD-9
43644	Laparoscopy, surgical, gastric restrictive procedure with gastric bypass and Roux-en-Y gastroenterostomy (roux limb 150 cm or less)	RYGB	CPT-4
43645	Laparoscopy, surgical, gastric restrictive with gastric bypass and small intestine reconstruction to limit absorption	RYGB	CPT-4
43844	Laparoscopic gastric restrictive procedure with gastric bypass and Roux en Y gastroenterostomy	RYGB	CPT-4
S2085	Lap GASTRIC BYPASS	RYGB	HCPC
43843	Gastric restrictive procedure, without gastric bypass, for morbid obesity; other than vertical-banded gastroplasty	AGB	CPT-4
44.95	Laparoscopic gastric restrictive procedure Adjustable gastric band and port insertion	AGB	ICD-9
43770	Laparoscopy, surgical, gastric restrictive procedure: placement of adjustable gastric band	AGB	CPT-4
S2082	Lap Band	AGB	HCPC
Procedure Assignment Rules: We will assign the specific bariatric procedure type based on ICD-9, CPT-4, and HCPCS procedure codes and the following rules that have been successfully applied in our prior studies:			
i. If only one code is present on the same day for the first bariatric procedure for a given patient, we assume that is the correct procedure assignment ii. If two or more codes are present on the same day for the first bariatric procedure for a given patient and they correspond to the same procedure type (e.g., RYGB, AGB, SG) then we assume that is the correct procedure assignment			

Code	Description	Procedure Assignment	Code type
iii. If two or more codes are present on the same day and they disagree on procedure type, we exclude that case			

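### Table 2 lets residual procedure codes decide the arm on their own (43843 as AGB; 44.38 and 44.39 as RYGB), and no planned count or sensitivity analysis would show how many patients depend on them

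*SAP*

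**What the plan says.** SAP Table 2 maps 17 codes to the three procedures: four to AGB, ten to RYGB and three to SG. Five of them matter here.

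- **43843, mapped to AGB:** "Gastric restrictive procedure, without gastric bypass, for morbid obesity; other than vertical-banded gastroplasty".
- **44.39, mapped to RYGB:** "Other gastroenterostomy; Bypass gastroduodenostomy; gastroenterostomy; gastrogastrostomy; Gastrojejunostomy without gastrectomy NOS".
- **44.38, mapped to RYGB:** "Laparoscopic gastroenterostomy; Bypass: gastroduodenostomy; gastroenterostomy; gastrogastrostomy; Laparoscopic gastrojejunostomy without gastrectomy NEC".
- **43633, mapped to RYGB:** "Gastrectomy, partial, distal; with Roux-en-Y reconstruction".
- **43.89, mapped to SG:** "Partial gastrectomy with bypass gastrogastrostomy; Sleeve resection of stomach".

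Three assignment rules follow. Rule i begins "If only one code is present on the same day for the first bariatric procedure for a given patient, we assume that is" and goes on to treat that code as the right assignment. Rule ii accepts several same-day codes that point to one procedure. Rule iii reads "If two or more codes are present on the same day and they disagree on procedure type, we exclude that case". The SAP supports the rules by stating that they worked in the team's earlier studies; it gives no validation figure.

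**The concern.** A code that alone decides the arm should describe that procedure and not others. The wording of 43843 covers any restrictive operation for obesity that is neither a bypass nor a vertical-banded gastroplasty. A sleeve fits that wording as well as a band does. The wording of 44.38 and 44.39 covers several gastric connections and names neither Roux-en-Y nor obesity.

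Two errors are possible. A sleeve recorded only as 43843 would be analysed as a band. A gastric operation done for another reason, in a patient who happens to have a BMI of at least 35, would be analysed as a primary RYGB or, through 43.89, as SG. The first blurs the AGB versus SG contrast and contaminates AGB versus RYGB. The second could bring into the RYGB or SG arm patients whose reoperation, readmission and mortality risks are not those of bariatric patients. Propensity scores and covariate adjustment repair neither, because both take the arm label as given.

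**Working it through.** The SAP states no figure on this point, so there is none to reproduce. The check is of wording, then of rules, then of safeguards, with an illustration of size at the end.

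**1. Wording against assigned arm**

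| Code | Arm | Names the assigned procedure? |
|---|---|---|
| 43843 | AGB | No band named; residual class for obesity |
| 44.39 | RYGB | Neither Roux-en-Y nor obesity named |
| 44.38 | RYGB | Laparoscopic counterpart of 44.39; same gap |
| 43633 | RYGB | Roux-en-Y named, but as reconstruction after a distal gastrectomy |
| 43.89 | SG | Sleeve resection named, but alongside a different gastrectomy |

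The other AGB codes (43770, 44.95, S2082) do name a band; 43770, for example, reads "Laparoscopy, surgical, gastric restrictive procedure: placement of adjustable gastric band". The only CPT code for SG, 43775, is laparoscopic. An open sleeve therefore has no CPT code of its own in Table 2, and by wording it fits 43843.

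**2. Code patterns run through the rules**

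- 43843 alone: AGB under rule i, whatever was done.
- 43843 with 43775, 43.82 or 43.89: excluded under rule iii (and exclusion criterion 2). The conflict comes only from the AGB label, since the two descriptions can both be true of one sleeve operation.
- 44.38 or 44.39 alone: RYGB under rule i.
- 44.39 with 43633: RYGB under rule ii, although neither describes a gastric bypass for obesity.

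**3. Safeguards elsewhere in the SAP**

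The inclusion criteria require a BMI of at least 35 in the prior year. The exclusion criteria remove patients with a listed gastrointestinal cancer code or a fundoplasty in the prior year, and those with an Emergency Department visit on the day of surgery. These reduce wrongful enrolment. None requires an obesity diagnosis, and none tests the arm when 43843 is the only code. Table 3 excludes uncommon procedures only by its listed codes, and 43843 is not among them.

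The sensitivity analyses named in the SAP concern calendar year, endoscopy, missing BMI, missing blood pressure, race or ethnicity, and integrated health systems. None varies the code map.

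**4. Illustration of size (all inputs assumed; none is in the SAP)**

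Let f be the share of the AGB arm that is really SG, and suppose these are average SG patients. The observed AGB-SG mean difference is then (1 − f) times the true one. With assumed 5-year reoperation risks of 30% (AGB) and 10% (SG), the observed AGB risk is 30(1 − f) + 10f:

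- f = 0.05: 28.5 + 0.5 = 29%, ratio 2.9
- f = 0.10: 27 + 1 = 28%, ratio 2.8
- f = 0.15: 25.5 + 1.5 = 27%, ratio 2.7

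The undistorted ratio is 30/10 = 3.0.

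To see how f arises, let q be the share of true SG patients labelled AGB and R the SG:AGB ratio. Then f = qR/(1 + qR):

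| R | q = 1% | q = 5% | q = 10% |
|---|---|---|---|
| 1 | 1.0% | 4.8% | 9.1% |
| 4 | 3.8% | 16.7% | 28.6% |
| 8 | 7.4% | 28.6% | 44.4% |

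For q = 5% and R = 4: 0.20/1.20 = 16.7%, so 83.3% of the true mean difference remains. If AGB is much the smaller arm, a low error rate among sleeves becomes a large share of it.

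**The case against.** A reader might infer that patients are in fact misassigned and that the AGB-SG estimates are known to be biased. The SAP does not support that: it gives no code counts and no error rate, and a one-line description does not show how 43843 was used in 2005-2015. The team's earlier experience with the rules may be good evidence, but it is not shown. This stands, and it limits the point to what can happen.

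It is also fair that the five codes are not equally weak. 43.89 names a sleeve and 43633 names Roux-en-Y, so these are ambiguous rather than silent. 43843 is itself worded for obesity, so wrongful enrolment of a non-obesity operation is not the worry there. The cancer exclusion removes an obvious non-bariatric use of the gastrectomy and gastroenterostomy codes. Rule iii keeps a sleeve with a second, sleeve code out of the AGB arm, though by discarding the patient.

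A further inference would be that 43843 should count as AGB only beside a band code. That amounts to deleting it, since the band codes already assign AGB. All three band codes are described as laparoscopic, so an open band would lose its only route into the arm. Likewise, 44.38 is the only laparoscopic ICD-9 code for RYGB, and removing it outright could lose genuine bypasses unevenly across sites.

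Finally, the SAP shows that Aims 1 and 2 had been analysed when this version was written, and its plan for data queries describes repeated testing before code goes to sites. A late change of cohort is not free. None of this answers the gap itself: nothing planned would show whether the residual codes decide few patients or many.

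**Conclusion.** The concern holds as a weakness of definition, not as a demonstrated bias. Under Table 2 and rule i, 43843, 44.38 and 44.39 each decide the arm alone although their wording does not identify the procedure; 43633 and 43.89 share the problem to a lesser degree. Patients can be put in the wrong arm or wrongly enrolled, and probable sleeve patients coded with 43843 are dropped under rule iii without a real conflict.

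The size is unknown. The figures above rest on assumed values of f, q, R and the two risks, on one-way mislabelling of sleeves as bands, and on mislabelled patients being typical SG patients. On those assumptions the AGB-SG difference is attenuated and keeps its sign. The effect of wrongful enrolment on RYGB and SG outcomes cannot be quantified from the document. The point warrants a check and limited changes to the rules, not removal of 43843 from the primary definition.

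**What to change.** 1. Report the number of patients in each arm by deciding code.
2. Add a sensitivity analysis of the primary outcome of each of Aims 1 to 3, restricted to patients with a procedure-specific code: 43770, 44.95 or S2082 for AGB; 43775 or 43.82 for SG; and, for RYGB, the codes that name gastric bypass or a restrictive procedure with Roux-en-Y (44.31, 43644, 43645, 43844, 43846, 43847, S2085).
3. Where 43843 appears with a sleeve-specific code (43775 or 43.82), assign SG instead of excluding the patient.
4. Where 44.38, 44.39, 43633 or 43.89 is the only Table 2 evidence that day, require an obesity diagnosis on the index encounter.

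The cost is one extra run, a change to the cohort program for items 3 and 4, and some loss of patients who have only non-specific codes, possibly uneven across sites. The restricted run would also lose any open bands coded 43843. For that reason, dropping patients with 43843 alone belongs in the sensitivity analysis and not in the primary cohort definition. If the counts in item 1 prove small, they will settle the matter by themselves.
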